6.3.2 Secondary Efficacy Endpoints

6.3.2.1 Percentages of Subjects with Reduction in Number of Migraine Days per Month

In analyses by months, subjects must (1) achieve the reduction criterion from OP in the number of migraine days in the specified month, (2) be evaluable (i.e., have ≥ 14 days of efficacy data [not necessarily consecutive]) in the specified month, and (3) have ≥ 1 migraine day (absolute not prorated to 28 days) of appropriate migraine severity in the OP analysis period to be classified as responders in the specified month. Otherwise, subjects are classified as failures in the specified month.

In analyses of the overall DBT (or overall OLE), subjects must (1) achieve the reduction criterion from OP in the number of migraine days in the overall DBT (or overall OLE), and (2) have ≥ 1 migraine day (absolute not prorated to 28 days) of appropriate migraine severity in the OP analysis period to be classified as responders. Otherwise, subjects are classified as failures.

Percentages of Subjects with Reduction in Migraine Days per Month in the DBT Phase

Analyses are based on the DBT migraine analysis set with eDiary efficacy dates in the OP and on-DBT efficacy analysis periods (see Section 6.3.1.1).

Treatment Group Comparisons

For each pain intensity (total; moderate or severe) and select percentage reductions ($\geq 50\%$, $\geq 75\%$, and 100%), the percentages of subjects with reductions are compared between treatment groups using Mantel-Haenszel risk estimation with stratification by randomization stratum (yes, no). This may be accomplished using SAS proc stdrate with the following options: method=mh, stat=risk, and effect=diff. Percentages are calculated against the number of subjects in the DBT migraine analysis set.

The table displays the following statistics at each month of the DBT Phase and overall DBT by pain intensity:

- Response rate (i.e., "n/N" and percentage), ASE, and 95% CI for each treatment group
- Stratified percentage difference between treatment groups (rimegepant placebo), ASE, 95% CI, and p-value
- Response rate (i.e., "n/N" and percentage), ASE, and 95% CI by randomization stratum for each treatment group
- Percentage difference between treatment groups (rimegepant placebo), ASE, 95% CI, and p-value by randomization stratum.

Results for \geq 50% reduction of moderate or severe migraine severity in the last 4 weeks (i.e., Month 3) support secondary objective #1. All other results support exploratory objective #2.

Subgroup analyses

Proportion of subjects with $\geq 50\%$ reduction from baseline in the number of moderate to severe migraine days will also be compared between treatment groups using a Mantel-Haenszel risk estimation with stratification by randomization stratum (yes, no) by subgroup of historical chronic migraine according to ICHD 3rd edition (yes or no) (Section 4.3). P-values are presented only for descriptive purpose.

The following statistics will be presented for each month in the DBT Phase and overall DBT mean by subgroup of historical chronic migraine according to ICHD 3rd edition (yes or no):

- Response rate (i.e., "n/N" and percentage), ASE, and 95% CI for each treatment group
- Stratified percentage difference between treatment groups (rimegepant placebo), ASE, 95% CI, and p-value.

Percentages of Subjects with Reduction in Migraine Days per Month in the OLE Phase

Analyses are based on the OL rimegepant migraine analysis set with eDiary efficacy dates in the OP and on-OL rimegepant efficacy analysis periods.

The frequency table of reductions from the OP in the number of migraine days per month in the OLE Phase is provided by treatment group/OL rimegepant and overall and by pain intensity (total; moderate or severe) in each month of the OLE Phase and overall OLE (see Section 6.3.1.2 for months), and displays the number and percentage of evaluable subjects in the following reduction categories: $\geq 50\%$, $\geq 75\%$, and 100%. Percentages are calculated against the number of evaluable subjects in the OL rimegepant migraine analysis set:

- In analyses by month, evaluable subjects are those with ≥ 1 migraine day of appropriate pain intensity in the OP and ≥ 14 days of eDiary efficacy data in the specified month.
- In analyses of the overall OLE, evaluable subjects are those with ≥ 1 migraine day of appropriate pain intensity in the OP.

Results support exploratory objective #5.

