3.2 Estimands

An estimand is the target of estimation to address the scientific question of interest posed by a study objective. The 4 attributes of an estimand include the population of interest, endpoint of interest, summary of the endpoint, and specification of how intercurrent events are reflected in the scientific question of interest.

For all objectives, the population of interest is defined through appropriate inclusion/exclusion criteria to reflect the targeted patient population for approval. Refer to the protocol for inclusion/exclusion criteria.

Intercurrent Events

Intercurrent events are those that occur after treatment initiation and either preclude observation of the endpoint or affect its interpretation.

Study drug discontinuation before the time point of interest defining the endpoint is considered an intercurrent event.

- For efficacy objectives assessed with a continuous endpoint during the DBT Phase, study drug discontinuation is handled with a "hypothetical strategy," i.e., the hypothetical scenario is that had subjects not discontinued DB study drug, their efficacy would have been similar to the efficacy of subjects from the same treatment group and randomization stratum who did not discontinue DB study drug. All observed values of the endpoint of interest are excluded after DB study drug discontinuation plus 1 day (see Section 7.2), and statistical methods are used to estimate the treatment effect that would have been seen had the intercurrent event not occurred.
- For efficacy objectives assessed with a binary endpoint during the DBT Phase, DB study drug discontinuation is handled with a "composite strategy," i.e., the occurrence of the intercurrent event is integrated as a component of the endpoint. All observed values of the endpoint of interest are excluded after DB study drug discontinuation plus 1 day (see Section 7.2), and subjects with missing data are considered failures.
- For efficacy objectives assessed during the OLE Phase, OL study drug discontinuation is handled with a "while-on-treatment strategy," i.e., response to treatment prior to the occurrence of the intercurrent event of interest. All observed values of the endpoint of interest are used on or before OL study drug discontinuation + 1 day (see Section 7.2).

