3.2.3 Exploratory Objective Estimands

The estimands corresponding to the exploratory objectives are shown in Table 3.

Objective 1	Mean reduction from baseline in the number of migraine days per month by intensity (total; moderate or severe) in each month and over the entire course of the DBT Phase
Efficacy Endpoint	Changes from the OP in the number of migraine days per month in each month and over the entire DBT Phase by pain intensity (total; moderate or severe)
Summary	Changes from the OP by treatment group using descriptive statistics and linear mixed effects model with repeated measures, and difference between treatment groups from the model for the DBT migraine analysis set
Intercurrent Events	Study drug discontinuation: hypothetical strategy
	Non-study prophylactic migraine medication use: treatment policy strategy
	Nonstudy acute migraine-specific medication use: composite strategy
	Use of nonstudy other medication to treat headache (migraine or nonmigraine) or aura: treatment policy strategy
Objective 2	Proportions of subjects with \geq 50% reduction, \geq 75% reduction, and 100% reduction from baseline in the number of migraine days per month by pain intensity (total; moderate or severe) in each month and over the entire course of the DBT Phase
Efficacy Endpoint	Proportions of subjects with $\ge 50\%$ reduction, $\ge 75\%$ reduction, and 100% reduction from the OP in the number of migraine days per month in each month and over the entire DBT Phase by pain intensity (total; moderate or severe)
Summary	Percentages by treatment group, and difference in percentages between treatment groups using Mantel-Haenszel risk estimation for the DBT migraine analysis set
Intercurrent Events	Study drug discontinuation: composite strategy
	Non-study prophylactic migraine medication use: treatment policy strategy
	Nonstudy acute migraine-specific medication use: composite strategy
	Use of nonstudy other medication to treat headache (migraine or nonmigraine) or aura: treatment policy strategy
Objective 3	Mean reduction from baseline in the number of migraine days per week by pain intensity (total; moderate or severe) in each week of the first 4 weeks of the DBT Phase
Efficacy Endpoint	Changes from the OP in the number of migraine days per week during DBT in each week of the first 4 weeks by pain intensity (total; moderate or severe)

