 - DBT migraine: subjects in the DBT efficacy analysis set with ≥ 14 days of eDiary data (not necessarily consecutive) in both the OP and ≥ 1 month (4-week interval) during the DBT Phase (see Section 6.3.1.1). This analysis set is used to assess migraine days, headache days, acute migraine-specific medication days, and acute migraine medication days during the DBT Phase.
 - DBT first month migraine: subjects in the DBT efficacy analysis set with ≥ 24 days of eDiary efficacy data (not necessarily consecutive) in both the OP and in first month (4week interval) of the DBT Phase (see Section 6.3.3.1). This analysis set is used to assess migraine and headache days per week during the DBT Phase.
- OL rimegepant efficacy: subjects in the DBT efficacy analysis set who take ≥ 1 dose of OL rimegepant. This analysis set is used to assess outcomes research endpoints during the OLE Phase.
 - OL rimegepant migraine: subjects in both the DBT migraine and OL rimegepant efficacy analysis sets with ≥ 14 days of eDiary efficacy data (not necessarily consecutive) in ≥ 1 month (4-week interval) in the OLE Phase. This analysis set is used to assess migraine days, headache days, acute migraine-specific medication days, and acute migraine medication days during the OLE Phase.

See Section 7.1 for derived dates and Section 7.2 for analysis periods.

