6.3.1 Reduction in Migraine Days per Month

Subjects are instructed to report headache occurrence, headache pain features and associated symptoms, aura occurrence, and medication used to treat headache or aura in the eDiary headache report every day in the OP, DBT, and OLE Phases.

Migraine days per month are assessed as "migraine days per 4 weeks" to correspond with the 4week visit schedule. Migraine days per month are based on 4-week intervals, and are prorated to account for missing migraine reports.

See Section 9.2.2 for the definition of eDiary efficacy data days, and Section 9.2.5 for the definition of migraine days.

6.3.1.1 Reduction in Migraine Days per Month in the DBT Phase: Primary Efficacy Endpoint

The number of migraine days per month in the DBT phase is examined relative to the number of migraine days per month in the OP for the DBT migraine analysis set, i.e., subjects with ≥ 14 days of eDiary efficacy data (not necessarily consecutive) in both the OP analysis period and ≥ 1 month (i.e., 4-week interval) in the on-DBT efficacy analysis period.

Months in the DBT phase are defined as follows:

- Month 1 (\leq 4 weeks; study days 1 to 28)
- Month 2 (> 4 to \leq 8 weeks; study days 29 to 56)
- Month 3 (> 8 to \leq 12 weeks; study days 57 to 84).

Analyses are based on eDiary efficacy dates in the OP and on-DBT efficacy analysis periods.

The number of migraine days per month is prorated to 28 days and derived as follows:

- OP: 28 × (total number of migraine days in the OP analysis period)/(total number of efficacy data days in the OP analysis period). Subjects must have ≥ 14 days of eDiary efficacy data (not necessarily consecutive) in the OP to be evaluable.
- Month (i.e., 4-week interval) in the on-DBT efficacy analysis period: 28 × (total number of migraine days in the month)/(total number of efficacy data days in the month). Subjects must have ≥ 14 days of efficacy data (not necessarily consecutive) in the specified month to be evaluable.
- Overall DBT: 28 × (total number of migraine days through Month 3 in the on-DBT efficacy analysis period)/(total number of efficacy data days through Month 3 in the on-DBT efficacy analysis period).

Missing Efficacy Data

The frequency table of missing efficacy data in the OP and DBT Phase is provided for the DBT efficacy analysis set, and displays the following categories:

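### The overall-DBT responder rule can count a subject who stopped double-blind drug after two weeks as a 12-week responder, which the declared composite strategy does not allow

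*SAP*

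**What the plan says.** All references are to the SAP, which is written for C4951021, the prevention study.

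- **Strategy.** Section 3.2 handles stopping double-blind drug, for binary endpoints in the DBT Phase, by building the stopping event into the outcome. Values later than one day after stopping are dropped, and "subjects with missing data are considered failures". Section 3.2.3, exploratory objective 2, covers the 50%, 75% and 100% responder endpoints in each month and over the whole DBT Phase, and lists "Study drug discontinuation: composite strategy".
- **By-month rule.** In Section 6.3.2.1 a responder in a given month must also "2) be evaluable (i.e., have ≥ 14 days of efficacy data [not necessarily consecutive]) in the specified month". Anyone else is a failure for that month.
- **Overall rule.** The next paragraph begins "In analyses of the overall DBT (or overall OLE), subjects must (1) achieve the reduction criterion from OP in the number of migraine days" and adds only the OP migraine-day condition.
- **Derivation.** Section 6.3.1.1 gives "Overall DBT: 28 × (total number of migraine days through Month 3 in the on-DBT efficacy analysis period", divided by the efficacy data days in the same period. That line states no minimum. Section 7.2 ends the on-DBT efficacy period one day after the last double-blind dose, or the day before open-label drug starts if that is earlier.
- **Who is counted.** Section 4.1 defines the DBT migraine set as "subjects in the DBT efficacy analysis set with ≥ 14 days of eDiary data (not necessarily consecutive) in both the OP and ≥ 1 month" of the DBT Phase. Section 6.3.2.1 adds: "Percentages are calculated against the number of subjects in the DBT migraine analysis set".

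**The concern.** The by-month rule puts the composite strategy into effect: a subject who stops before a month has too few diary days in it and fails. The overall rule has nothing equivalent. Because the overall value is a ratio over available days, it exists for everyone in the analysis set, so the missing-equals-failure step never applies. An early stopper is judged on the days before stopping, and that result stands for the whole phase. This is in effect a while-on-treatment strategy, which Section 3.2 treats as a separate strategy and does not assign to binary DBT endpoints.

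At stake is whether the reported overall-DBT response rates, differences, confidence intervals and p-values estimate what the SAP says they estimate. They are produced for three reduction thresholds and two pain-intensity categories. The 50% moderate-to-severe comparison is repeated by historical chronic migraine. If early stopping differs between arms, the departure from the declared estimand differs too.

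**Working it through.** **The plan's own figures.** The SAP states no expected rate or power for this endpoint. Its only power figure, in Section 5, concerns the primary endpoint (difference 1 day, SD 3.75, 225 evaluable per arm, two-sided 0.05, roughly 80%). It reproduces: 1 / (3.75 × √(2/225)) = 2.83, and Φ(2.83 − 1.96) = 80.7%. The point below does not depend on it.

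**Step 1: can an early stopper pass the rule as written?** Take a subject with 8 migraine days per 28 in the OP, last double-blind dose on day 13, and a complete diary.
- On-DBT efficacy period (Section 7.2): days 1 to 14, so 14 efficacy data days.
- Analysis set (Section 4.1): 14 days in Month 1 is enough, so the subject is included.
- Overall value (Section 6.3.1.1), with 2 migraine days: 28 × 2 / 14 = 4.
- Reduction: (8 − 4) / 8 = 50%. The subject meets the 50% criterion.
- Months 2 and 3: no diary days, so failure in both.
- Month 3 covers "study days 57 to 84", so the phase is 84 days. The 12-week result rests on 14 / 84 = 16.7% of it.

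With no migraine days in those 14 days, the same subject would be a 100% responder over 12 weeks. Under the composite strategy the subject fails in either case.

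**Step 2: how easily does a short record pass?** This is an illustration with assumed inputs: a constant daily migraine probability equal to the OP rate, no true change, and P(X ≤ m) for X ~ Binomial(days, OP/28). Here m is the largest count whose prorated value is at most half the OP value.

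| OP migraine days per 28 | m at 14 days | chance at 14 days | m at 84 days | chance at 84 days |
|---|---|---|---|---|
| 4 | 1 | 38.5% | 6 | 3.5% |
| 8 | 2 | 19.0% | 12 | 0.2% |
| 12 | 3 | 8.6% | 18 | <0.01% |

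**Step 3: does that direction always hold?** A less idealised simulation assumes daily probability Beta(6, 12.7), 4 to 18 OP migraine days, and a between-period log-SD of 0.25. The chance of at least a 50% reduction is:

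| True reduction | 15 diary days | 84 diary days |
|---|---|---|
| 0% | 14.3% | 5.5% |
| 20% | 25.0% | 14.5% |
| 60% | 65.3% | 71.4% |
| 70% | 78.1% | 87.9% |

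Short records pass the 50% threshold more often when the true reduction is small, and less often when it is large.

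**Step 4: effect on an arm's rate.** Fall in the rate = (share of the set that stops early) × (share of those who meet the criterion). The SAP gives neither. With assumed ranges of 2% to 10% and 20% to 60%, the fall runs from 0.02 × 0.20 = 0.4 points to 0.10 × 0.60 = 6.0 points. The between-arm difference moves only by the gap between the two arms' falls, so it does not move if they are equal.

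**The case against.** The strongest reply is that Section 3.2 carries out the composite strategy in two operations: drop data after stopping, then fail subjects whose data are missing. The prorated overall value is never missing for a subject in the set, so the rule follows those operations literally. It is true that the text never says in so many words that a discontinuer fails the overall endpoint. On this reading, however, stopping drug has no bearing on the outcome. That is not what Section 3.2 says a composite strategy is, and it removes the difference from while-on-treatment.

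Other objections stand and limit the point:

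- The rule is not wholly without a diary floor. Section 4.1 requires 14 days in at least one DBT month, which is where the two weeks come from.
- A reader might extend the criticism to the overall OLE rule, which shares the sentence. The SAP does not support that: Sections 3.2 and 3.2.3 (exploratory objective 5) declare while-on-treatment there, and judging subjects on data up to stopping is what that strategy intends.
- A reader might ask for 14 diary days in each of Months 1 to 3. That goes beyond the composite strategy. A subject who completes 12 weeks on drug with 28 + 28 + 13 = 69 diary days would fail without having discontinued.
- A reader might infer that early stoppers are always favoured, or that the bias always helps the arm with more stopping. Step 3 shows the comparison with full records reversing at the 50% threshold when the true reduction is large.
- The results are exploratory, unadjusted and descriptive. The monthly rates stand in the same table, and evaluability by month is tabulated separately.

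**Conclusion.** The point holds, as a minor one. For responder endpoints over the whole DBT Phase, the rule in Section 6.3.2.1 does not deliver the composite strategy assigned in Sections 3.2 and 3.2.3, and in effect applies while-on-treatment. Step 1 establishes this from the SAP's definitions alone; the example subject's values are hypothetical.

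The reach is narrow: the exploratory overall-DBT responder results and their chronic-migraine subgroup version. Secondary objective 1 uses Month 3 with its own 14-day rule, so a two-week stopper already fails there and the testing hierarchy is untouched. A corrected rule would leave each arm's rate the same or somewhat lower. By how much cannot be computed, because the SAP gives no discontinuation rate; the 0.4 to 6.0 points rest wholly on assumed ranges.

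The point rests on the C4951021 SAP alone. The protocol supplied is for C4951022, a single-dose acute-treatment study with no such endpoint. Neither the C4951021 protocol nor the Core SAP was available to check.

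**What to change.** Add one sentence to the overall-DBT responder rule in Section 6.3.2.1: subjects who did not complete the DBT Phase, meaning that double-blind drug was discontinued before Week 12, are classified as failures for overall DBT. Separate the DBT and OLE rules, which now share a sentence, so that the addition does not carry over to overall OLE. Do not add a diary-day minimum for each month.

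If the sponsor does want overall DBT judged on data up to stopping, the alternative is to restate the strategy for that endpoint in Sections 3.2 and 3.2.3 as while-on-treatment.

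The cost is a small text edit and one added condition in the program. Section 6.2.3.3 already derives DBT completion from the DB Subject Status CRF, so no new data are needed. Sample size, the primary analysis and the testing hierarchy do not change.

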3.2.2 Secondary Objective Estimands

The estimands corresponding to the secondary objectives are shown in Table 2.

Table 2	Secondary	Objective	Estimands

Objective 1	Proportion of subjects with $\geq 50\%$ reduction from baseline in the number of moderate to severe migraine days per month in the last 4 weeks of the DBT Phase
Efficacy Endpoint	Proportion of subjects with \geq 50% reduction from OP in number of moderate or severe migraine days per month in the last 4 weeks (Weeks 9 to 12) of the DBT Phase
Summary	Percentage by treatment group and difference in percentages between treatment groups using Mantel-Haenszel risk estimation for the DBT migraine analysis set
Intercurrent Events	Study drug discontinuation: composite strategy
	Non-study prophylactic migraine medication use: treatment policy strategy
	Nonstudy acute migraine-specific medication use: composite strategy
	Use of nonstudy other medication to treat headache (migraine or nonmigraine) or aura: treatment policy strategy
Objective 2	Mean reduction from baseline in the number of migraine days per month over the entire course of the DBT Phase
Efficacy Endpoint	Mean change from OP in the number of migraine days per month over the entire DBT Phase (Weeks 1 to 12)
Summary	Change from OP by treatment group using descriptive statistics and linear mixed effects model with repeated measures, and difference between treatment groups from the model for the DBT migraine analysis set
Intercurrent Events	Study drug discontinuation: hypothetical strategy
	Non-study prophylactic migraine medication use: treatment policy strategy
	Nonstudy acute migraine-specific medication use: composite strategy
	Use of nonstudy other medication to treat headache (migraine or nonmigraine) or aura: treatment policy strategy
Objective 3	Mean reduction from baseline in the number of migraine days per month in the first 4 weeks of the DBT Phase
Efficacy Endpoint	Mean change from OP in the number of migraine days per month in the first 4 weeks (Weeks 1 to 4) of the DBT Phase
Summary	Change from OP by treatment group using descriptive statistics and linear mixed effects model with repeated measures, and difference between treatment groups from the model for the DBT migraine analysis set
Intercurrent Events	Study drug discontinuation: hypothetical strategy
	Non-study prophylactic migraine medication use: treatment policy strategy
	Nonstudy acute migraine-specific medication use: composite strategy

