7 CONVENTIONS

7.1 Derived Dates

Derived dates are defined as follows:

- Screening visit date: visit date from the Visit Date SS CRF with folder name "Screening Visit"
- eDiary efficacy date: complete datepart{eDiary finding date/time} 1 day from the eDiary headache report
- Study drug start date: earliest complete dose date from IP Administration DB or OL CRF with number of tablets taken > 0. This is an analysis period reference date.
- Study drug end date: latest complete dose date from IP Administration DB or OL CRF with number of tablets taken > 0
- Study drug last date:
 - Before the final database lock: study drug end date derived only for subjects who have either (1) or (2):
 - (1) "Yes" or "no" response to the phase completion question on the DB Subject Status CRF, and {either (1a) "no" response to the continuing to the next phase question on the DB Subject Status CRF, or (1b) "Follow-up" specified as the next phase on the DB Subject Status CRF}, and missing OL rimegepant start date
 - (2) "Yes" or "no" response to the phase completion question on the OLE Subject Status or Follow-up Subject Status CRF
 - Final database lock: study drug end date

This is an analysis period reference date.

- DB study drug start date: earliest complete dose date from IP Administration DB or OL CRF records with number of tablets taken > 0 and valid DB wallet number. This is an analysis period reference date.
- DB study drug end date: latest complete dose date from IP Administration DB or OL CRF records with number of tablets taken > 0 and valid DB wallet number
- DB study drug last date:
 - Before the first database lock: DB study drug end date derived only for subjects with "yes" or "no" response to the phase completion question on the DB Subject Status, OLE Subject Status, or Follow-up Subject Status CRF
 - First database lock or after: DB study drug end date

This is an analysis period reference date.

• OL rimegepant start date: earliest complete dose date from IP Administration – DB or OL CRF records with number of tablets taken > 0 and valid OL wallet number. This is an analysis period reference date.

- OL rimegepant end date: latest complete dose date from IP Administration DB or OL CRF records with number of tablets taken > 0 and valid OL wallet number
- OL rimegepant last date:

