7.2 Analysis Periods

Measurements are slotted into analysis periods based on comparing measurement dates to analysis period reference dates (time is not applicable).

Analysis periods are defined according to endpoints as follows:

- eDiary efficacy endpoints (migraine days, acute migraine-specific medication days, acute migraine medication days, headache days)
 - OP: eDiary efficacy date on or after the OP start date through the OP end date. Note that this is a subset of the pretreatment analysis period.
 - 28-day OP: eDiary efficacy date on or after the OP start date through the earlier of {OP start date + 27 days; OP end date}. Note that this is a subset of the OP analysis period, and is used only to assess efficacy data issues during the OP as relevant protocol deviations.
 - On-DBT efficacy:
 - If the DB study drug last date or OL rimegepant start date is not missing: eDiary efficacy date on or after the DB study drug start date through the earlier of {DB study drug last date + 1 day; OL rimegepant start date 1 day}
 - If the DB study drug last date and OL rimegepant start date are both missing: eDiary efficacy date on or after the DB study drug start date

This period is used to assess efficacy during the DBT Phase.

- On-OL rimegepant efficacy:
 - If the OL rimegepant last date is not missing: eDiary efficacy date on or after the OL rimegepant start date through the OL rimegepant last date + 1 day
 - If the OL rimegepant last date is missing: eDiary efficacy date on or after the OL rimegepant start date
- Pretreatment characteristics and safety endpoints*
 - Pretreatment: This period is used to derive baseline values.
 - On-DBT safety: This period is used to assess safety endpoints on DBT for the DBT safety analysis set.
 - Post-DBT pre-OL rimegepant safety: This period is used to assess safety endpoints during the interim period (i.e., post-DBT pre-OL rimegepant) for the interim safety analysis set.
 - On-OL rimegepant safety: This period is used to assess safety endpoints on OL rimegepant for the OL rimegepant safety analysis set.
 - On-DB or OL rimegepant safety: This period is used to assess safety endpoints on DB or OL rimegepant for the DB or OL rimegepant safety analysis set.

- On-treatment safety: This period is used to define analysis visit windows.
- Follow-up safety: This period is used to assess safety endpoints during follow-up for the follow-up safety analysis set.
- Outcomes research endpoints (MSQoL, MIDAS, EQ-5D-5L) *

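### The responder analysis for secondary objective #1 drops the earliest drug stoppers from its denominator, although the stated composite strategy would count them as failures

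*SAP*

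**What the plan says.** All references are to the SAP, which is written for C4951021 (prevention). The protocol supplied is for C4951022 (acute treatment), so the point can be checked only within the SAP.

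- **Strategy.** Table 2 in Section 3.2.2 gives, for secondary objective #1, "Study drug discontinuation: composite strategy". Section 3.2 explains this for binary endpoints in the double-blind treatment (DBT) phase: "the occurrence of the intercurrent event is integrated as a component of the endpoint". Values after discontinuation plus 1 day are excluded, and "subjects with missing data are considered failures".
- **Denominator.** Section 6.3.2.1: "Percentages are calculated against the number of subjects in the DBT migraine analysis set". Table 2 names the same set.
- **Entry to that set.** Section 4.1 admits "subjects in the DBT efficacy analysis set with ≥ 14 days of eDiary data (not necessarily consecutive) in both the OP and ≥ 1 month" of the DBT phase. Section 6.3.1.1 confirms that the month is counted inside the on-DBT efficacy analysis period.
- **End of usable data.** Section 7.2 runs that period "through the earlier of {DB study drug last date + 1 day" or the day before open-label start. Section 7.1 sets the last date from lock onward: "First database lock or after: DB study drug end date".
- **Responder rule.** Section 6.3.2.1 requires the reduction, at least 14 efficacy-data days in the month, and at least one qualifying migraine day in the observation phase (OP). Anyone else in the set is a failure.

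**The concern.** Under a composite strategy, stopping drug is itself an unfavourable outcome. Here the same event is handled in two opposite ways depending on when it happens: a very early stopper disappears from numerator and denominator, and a somewhat later one is a failure. Membership of the denominator depends on the intercurrent event, so calling the migraine set the population of interest does not remove the conflict.

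This endpoint is the first tested after the primary, at two-sided 0.05, and every later secondary test depends on it (Section 5). The jump-to-reference and tipping-point analyses in Section 6.3.1.1 use the wider DBT efficacy set but cover the primary endpoint only. Nothing in the SAP would show how much the responder result depends on the exclusions.

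**Working it through.** **The SAP's own figure.** Section 5 gives about 80% power for the primary with 225 evaluable per arm, a 1-day difference, SD 3.75 and two-sided 0.05. Check: 1/(3.75 × √(2/225)) = 2.83, and Φ(2.83 − 1.96) = 0.81. This reproduces. The SAP states no rates and no power for the responder endpoint, so rates below are assumptions.

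**Step 1: who leaves the denominator.** Take study day 1 as the first double-blind dose (the formal definition is in the Core SAP, not supplied) and assume a complete diary. A last dose on day L gives usable days 1 to L + 1. The DBT months are days 1–28, 29–56 and 57–84.

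| Last dose | Usable days | Handling |
|---|---|---|
| Day 1 to 12 | at most 13 | not in the migraine set |
| Day 13 to 68 | at least 14 in some month, at most 13 in Month 3 | in the set, Month 3 failure |
| Day 69 or later | at least 14 in Month 3 (day 69: days 57 to 70) | in the set, judged on the reduction |

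On every-other-day dosing the first row means a last dose on day 11 or earlier. Missed diary entries move the cut-off later.

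**Step 2: effect on the difference.** Let p be the responder rate in the analysed set and e the fraction removed for early stopping, for rimegepant (R) and placebo (P). Then:

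- SAP difference = pR − pP
- composite difference = pR(1 − eR) − pP(1 − eP)
- overstatement = pR·eR − pP·eP

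Assume 245 per arm (the randomized number in Section 5, taken as all treated), pR = 50% and pP = 40%, so the SAP difference is 10.0 points:

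| Early stoppers, R and P | Overstatement | Composite difference |
|---|---|---|
| 5 and 5 | (2.5 − 2)/245 = 0.2 | 9.8 |
| 10 and 10 | (5 − 4)/245 = 0.4 | 9.6 |
| 10 and 5 | (5 − 2)/245 = 1.2 | 8.8 |
| 15 and 5 | (7.5 − 2)/245 = 2.2 | 7.8 |
| 5 and 10 | (2.5 − 4)/245 = −0.6 | 10.6 |

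At these rates the sign changes once placebo has more than 50/40 = 1.25 times as many early stoppers as rimegepant.

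**Step 3: effect on the test.** Assume the composite rate is 40% in both arms, that is 98 responders out of 245 each. Normal approximation, strata ignored:

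- 10 versus 5: 98/235 = 41.7% and 98/240 = 40.8%. Difference 0.9 points, SE 4.5 points, two-sided rejection about 5.4%.
- 15 versus 5: 98/230 = 42.6% and 98/240 = 40.8%. Difference 1.8 points, SE about 4.6 points, rejection about 6.8%.

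**The case against.** **Most stoppers are handled as declared.** This is correct. With complete diaries, a last dose from day 13 to day 68 gives a Month 3 failure. The gap is confined to about the first 12 of 84 days, which limits its size but does not remove the conflict.

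**The set is disclosed and exclusions will be visible.** Also true: Table 2 names it, Section 6.3.1.1 tabulates exclusions, and Section 6.3 lists them with reasons. However, the category shown is fewer than 14 diary days in all three months, which does not separate stopping drug from poor diary use, and no alternative estimate is planned.

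**Late stoppers.** A reader might infer that the plan also breaks its composite strategy at the other end, because a subject who stops on day 69 or later can still be a responder. The documents do not establish this. Section 3.2 limits the event to discontinuation that precedes the time point defining the endpoint, and the endpoint here is an interval, Weeks 9 to 12. Whether stopping inside that interval qualifies is not stated. That is an ambiguity to resolve, not a demonstrated departure.

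**Size.** A reader might also treat the whole planned loss from 245 to 225 per arm (20 each, 40 in total) as early stoppers and split it unevenly. For example, 28 versus 12 with a true composite rate of 41% gives 0.41 × 245/217 = 46.3% against 0.41 × 245/233 = 43.1%, a false 3.2 points and rejection near 10%. Section 5 does not support that reading. The loss is from randomized to evaluable, which can also include untreated subjects, short OP diaries and poor diary use, and nothing in the SAP suggests that split or its direction.

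**Conclusion.** The point holds for early stoppers. The declared strategy and the denominator in Section 6.3.2.1 conflict, and subjects whose last dose is on about day 12 or earlier are removed where the strategy would fail them.

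The effect is probably small and its direction is unknown: about 0.2 to 0.4 points overstatement with equal early stopping of 5 to 10 per arm, and about 1 to 2 points with the moderate imbalances shown. It favours rimegepant if that arm loses more, and becomes conservative if placebo loses sufficiently more. Rejection of about 5.4% to 6.8% applies to this single test under an equal composite rate of 40%; the test counts only after the primary succeeds. These figures rest on assumed responder and stopping rates, complete diaries, and 245 treated subjects per arm. They do not support a claim that the result will be biased in favour of rimegepant or that the error rate is doubled. Because the endpoint is alpha-controlled and has no sensitivity analysis, the conflict should still be settled before unblinding.

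**What to change.** 1. Analyse this responder endpoint on the DBT efficacy analysis set already defined in Section 4.1 (randomized only once, at least one double-blind dose), without the post-baseline 14-day entry condition.
2. Classify as a failure every subject with fewer than 14 evaluable Month 3 days, including those who reach 14 days in no month.
3. State the rule for subjects with fewer than 14 OP days, who have no evaluable baseline. Either keep the OP condition, which concerns pre-treatment data and does not depend on stopping drug, or count them as failures.
4. Keep the DBT migraine set as a supportive analysis.
5. State whether stopping double-blind drug within Weeks 9 to 12 precedes the time point of interest. If it does, define the failure from the DB study drug last date. DBT phase non-completion (Section 6.2.3.3) is not a substitute: it rests on a phase-completion answer, and a missing answer counts as non-completion after lock.

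The cost is SAP wording, a changed denominator and, if item 5 is answered yes, one added responder condition. The analysis set and dose dates are already defined. Response rates will be slightly lower in both arms.
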